3.7.2. Treatment Exposure

Duration of exposure (ALKS 3831 and olanzapine) will be defined as the number of days from the date of the first dose of study drug taken to the date of the last dose taken, inclusive (ie, last dose date – first dose date + 1). Duration of exposure will be summarized for the Safety Population by treatment group.

The overall mean and modal dose of olanzapine will be summarized by treatment group. The proportion of subjects at each olanzapine dose level at randomization and at final dose will also be summarized by treatment group.

3.8. Efficacy Analyses

3.8.1. General Considerations

Only the on-treatment weight assessments will be included in the analyses, unless specified otherwise.

3.8.2. Primary Efficacy Endpoint

The primary efficacy endpoint is:

- Percent change from baseline in body weight at Week 12

3.8.2.1. Primary Analysis

The null hypothesis is that there is no difference in percent change from baseline in body weight at Week 12 between ALKS 3831 and olanzapine. The alternative hypothesis is that there is a difference between ALKS 3831 and olanzapine.

The primary endpoint will be analyzed by analysis of covariance (ANCOVA) with the multiple imputation (MI) method for handling of missing values. The model will include the treatment group and randomization strata (diagnosis [schizophrenia/schizopreniform disorder vs bipolar I disorder], region [US vs non-US] and baseline BMI [<25 vs ≥ 25 kg/m²]) as factors, and the baseline weight as the covariate. Only the on-treatment measurements will be included in the analysis. The following steps will be performed:

1. The missing data on body weight will be imputed using MI. If there is any subject whose missing data pattern is non-monotonic (defined as having missing data in between visits), the Markov Chain Monte Carlo (MCMC) method will be used to impute the data to a monotonic missing pattern (i.e., if the data is missing at the current visit, the data at all following visits are missing). A single Markov chain will be used with 200 burn-in iterations, 100 iterations between imputations and a Jeffrey's prior. Next, the missing data will be imputed sequentially by each visit using a regression method. The imputation regression model includes treatment group, all randomization strata as factors, and body weight at all previous visits (including baseline weight) as covariates. At least 100 imputations will be carried out. More imputations may be performed to improve the precision. The initial seed for both steps of the imputation will be 8704011.
2. Percent change from baseline in weight at Week 12 of each of these multiple imputed datasets will be analyzed by the ANCOVA model with treatment group, all randomization strata as factors, and the baseline weight as covariate.
3. Results from Step 2 will be combined using Rubin's method. Estimated treatment effect, standard error (SE), 95% CI, and p-value will be reported.

Descriptive statistics of body weight and percent change from baseline at each visit (including last assessment during treatment period) will be presented by treatment group based on observed and MI data.

3.8.2.2. Sensitivity Analysis

To assess the robustness of the primary analysis, the following sensitivity analyses will be performed:

- **Delta-adjusted pattern mixture model:** To assess the potential impact of missing data due to missing not at random (MNAR), the delta-adjusted Pattern Mixture Model (Ratitch et al, 2013) will be conducted to assess the impact of missing data. It incorporates the clinical assumption that olanzapine subjects who discontinue at a given time point would have, on average, their unobserved weight gain decreased by some amount δ compared with the observed weight gain of subjects on the olanzapine arm who continue to the next time point. Subjects who discontinue from the ALKS 3831 arm would have the same weight gain trajectory as the ALKS 3831 subjects who stay on the study. A sequential regression-based MI procedure will be used to incorporate the assumption and to allow uncertainty in the imputations to be reflected appropriately in the analysis. The imputation model will use the measurement at the current time point as the response variable and include the measurements at the previous time points as covariates and all randomization strata as factors. One hundred imputations will be carried out. For each of the 100 imputed data sets, the same ANCOVA model as in the

primary analysis will be fitted to the percent change from baseline at Week 12 to obtain the treatment effect estimate and standard error. Rubin's rule will be used to combine the treatment effect estimates and standard errors across imputations. The shift parameters will account for 10%, 20%, 30%, 40%, 50%, and up to 100% of the observed treatment difference between olanzapine and ALKS 3831 from the primary analysis of the percent change from baseline in body weight at Week 12 in FAS population.

- **Including on and off-treatment assessments:** To further assess the potential impact of missing data due to MNAR, the primary analysis will be repeated including both on-treatment and off-treatment weight assessments after premature discontinuation of study drug.
- **Additional covariates:** The ANCOVA and MI approach may adjust for additional covariates and/or factors, including but not limited to study sites.
- **Average treatment effect:** Average treatment difference across visits through Week 12 between ALKS 3831 and olanzapine will be analyzed using mixed model with repeated measurements (MMRM) model. The MMRM model will include treatment, visit, treatment-by-visit interaction term, all randomization strata as categorical fixed effects; baseline weight will be included as a covariate. An unstructured covariance structure will be applied. The Kenward-Roger approximation ([Kenward and Roger 1997](#)) will be used to adjust the denominator degree of freedom. The analysis will be performed on all observed post-randomization on-treatment weight measurements without imputation of missing data.

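### The delta-adjusted imputation model leaves out treatment group and does not say it is fitted by arm, so as written it cannot deliver the arm-specific assumption it is meant to test

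*SAP*

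**What the plan says.** **Primary imputation (SAP 3.8.2.1).** "The missing data on body weight will be imputed using MI". The model is given in full: "The imputation regression model includes treatment group, all randomization strata as factors, and body weight at all previous visits (including baseline weight) as covariates".

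**Delta-adjusted imputation (SAP 3.8.2.2).** This bullet does not refer back to the primary model. It takes the measurement at the current time point as the response and will "include the measurements at the previous time points as covariates and all randomization strata as factors". Treatment group is not listed, and separate fitting by arm is not mentioned.

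**The assumption to be implemented (same bullet).** Olanzapine dropouts have their unobserved gain reduced by delta "compared with the observed weight gain of subjects on the olanzapine arm who continue to the next time point". For the other arm, "Subjects who discontinue from the ALKS 3831 arm would have the same weight gain trajectory as the ALKS 3831 subjects who stay on the study". The SAP adds: "A sequential regression-based MI procedure will be used to incorporate the assumption".

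**Size of the shift (same bullet).** "The shift parameters will account for 10%, 20%, 30%, 40%, 50%, and up to 100% of the observed treatment difference between olanzapine and ALKS 3831", taken from the "primary analysis of the percent change from baseline in body weight at Week 12 in FAS population".

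**Where the datasets go next.** SAP 3.8.3.1.2 derives the 10% weight-gain sensitivity analysis from the same imputed datasets. SAP 3.8.3.2 applies the same analyses to the 7% cutoff. SAP 3.8.3.3 carries the approach over to waist circumference.

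**The concern.** The assumption is arm-specific on both sides, and the listed model is not. If a programmer fits it once to all subjects, a dropout's later weights are predicted from a regression averaged over both arms. The only information about arm is what that subject's earlier weights happen to carry. Two things follow.

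- At zero shift the analysis no longer returns the primary estimate, because the imputation model has changed as well as the missing-data assumption.
- Each labelled shift comes on top of an unlabelled one caused by pooling. The percentage at which significance is lost then cannot be read as a departure from the primary assumption.

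This matters because it is one of two planned checks that the SAP labels as addressing data missing not at random, in a trial planned with 35% dropout. The other check repeats the primary analysis with off-treatment weights included.

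A smaller gap sits beside this one. The bullet does not name the scale of the imputed measurement. It also does not say whether the shift is applied once, at the first missed visit, or again at every missed visit.

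**Working it through.** **1. Planning values and the plan's own figure.** SAP 2 gives 8.5% against 5% gain (difference 3.5), SD 8, 35% dropout and 200 per arm. Completers: 200 × 0.65 = 130 per arm. SE = 8 × √(2/130) = 0.992, and 3.5/0.992 = 3.53. Power = Φ(3.53 − 1.96) = 94.1%. The stated power of at least 90% is reproduced. The sample size is not in question.

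**2. What pooling does.** Let g be the Week 12 gap between arms among imputed dropouts. The overall difference is

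0.65 × 3.5 + 0.35 × g.

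- Treatment in the model, or fitting by arm: g = 3.5, so the difference is 2.275 + 1.225 = 3.50.
- Pooled, with earlier weights carrying no information about arm: g = 0, so the difference is 2.28.
- Pooled, with earlier weights partly informative: between these two, unless the pooled regression projects an early gap forward by more than the true growth. Then g exceeds 3.5.

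**3. Size of g.** The documents give no trajectory, correlation or dropout timing, so all three are assumed. Visits are at Weeks 1, 2, 4, 6, 8, 10 and 12. Let d be the vector of arm differences by visit and S the within-arm covariance (SD 8 at Week 12). With 1:1 allocation the pooled covariance is A = S + dd′/4. The coefficients for visit v on earlier visits are b = A(earlier, earlier)⁻¹ A(earlier, v). After dropout the gap follows g(v) = b · g(earlier).

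Dropout is unrelated to outcome. The first missed visit is Week 2 or later, because the FAS requires a postbaseline weight. Timing is early-weighted, uniform or late-weighted. Strata and baseline weight are left out because randomization balances them. Week 12 difference at zero shift, range over the three timings:

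| Within-arm covariance | Gap linear in time | Square-root | Exponential, rate 1/4 per week |
|---|---|---|---|
| AR 0.7 per visit, SD 8 throughout | 2.41–2.64 | 2.48–2.73 | 2.50–2.77 |
| AR 0.9 per visit, SD 8 throughout | 2.55–2.85 | 2.71–2.99 | 2.75–3.06 |
| Brownian | 2.65–2.97 | 2.93–3.18 | 2.96–3.26 |
| AR 0.8, SD growing as √t | 2.57–2.84 | 2.81–3.02 | 2.83–3.08 |
| Random slope plus noise SD 2 | 2.89–3.25 | 3.42–3.72 | 3.46–3.84 |
| AR 0.95, SD growing as t | 3.27–3.35 | 3.69–4.05 | 3.83–4.13 |

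With treatment in the model every cell is 3.50. The first four rows (36 of 54 settings) lie between 2.41 and 3.26. Values above 3.5 occur only in the last two rows, with an early-separating gap.

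**4. Check by simulation.** The simulation used 40 trials of 200 per arm with 20 imputations each, linear gain and an assumed 70 kg mean baseline. Zero-shift differences were 3.40 with treatment in the model, 3.39 by arm and 2.80 pooled. The implied gap among dropouts is (2.80 − 0.65 × 3.40)/0.35 = 1.69, half of 3.40. This run let some subjects drop out before any postbaseline weight; they would not be in the FAS, so it shows direction and rough size only.

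**5. The unlabelled shift.** In the same simulation, with treatment in the model, a 100% shift left 2.17 if applied at the first missed visit (a fall of 1.23) and −1.41 if applied at every missed visit (a fall of 4.81). Pooling alone removed 3.40 − 2.80 = 0.60. That equals 0.60/1.23 = 49% or 0.60/4.81 = 12% of the full shift, before any shift is applied.

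**6. First missed visit or every missed visit.** Treatment in the model, 100% shift. Hand check for the Brownian case with uniform timing, where a shift carries forward in full and dropouts miss 3.5 visits on average:

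- once: 3.5 − 0.35 × 3.5 = 2.28
- every missed visit: 3.5 − 0.35 × 3.5 × 3.5 = −0.79

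Over the first five covariances and three timings, the remaining difference is about 2.0 to 3.1 (first missed visit only) against about −1.8 to +1.2 (every missed visit). Both ranges lie lower under the sixth, steeper covariance.

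**The case against.** **By-arm fitting is the evident intention.** The bullet compares like with like within each arm and says the procedure will carry that assumption. A regression run separately by arm would not list treatment as a predictor, so its absence is what by-arm fitting would look like. This is a fair reading and probably the right one. What stands against it is that the primary model handles arm by listing treatment group, while this model neither lists it nor says it is run by arm. Followed literally, the text gives an analysis that contradicts its own assumption.

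**Programming specifications may settle it.** SAP 8 places them in a separate document. But the SAP states the primary imputation down to its seed, so the predictors of this model belong in the SAP too.

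**Pooling is conservative.** It usually shrinks the difference, so a reader should not infer that the omission favours ALKS 3831. It is not always conservative, though, and even a conservative error leaves the shift percentages without a clear meaning.

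**The secondary gaps are easily made too large.**
- The wording about a given and a next time point leans towards visit-wise use. Nothing in it suggests a shift at Week 12 alone, so that option should not serve as one end of a contrast.
- A reader might infer an error of units, with percentage points subtracted from kilograms. If percent change is itself the imputed measurement, no conversion is needed; the SAP simply does not say.
- For waist circumference, the natural reading is that the shift is sized from the waist difference.

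**Conclusion.** The point holds as a defect in the stated imputation model of one sensitivity analysis. As written and fitted to both arms, the model cannot give each arm's dropouts the trajectory of that arm's continuers. At the SAP's planning values the zero-shift difference would be about 2.4 to 3.3 instead of 3.5 in most assumed settings, and up to about 4.1 in a few steep ones. Those figures rest on assumed trajectories, covariances and dropout timing, with dropout unrelated to outcome. They do not predict the trial's result. The 10% weight-gain sensitivity analysis inherits the same datasets, and the 7% analysis follows the same method.

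A reader might go further and infer that the primary result is in doubt. The documents do not support that: SAP 3.8.4 rests the positive-study claim on the primary analysis, whose imputation model includes treatment group.

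The timing and scale of the shift are a secondary clarification: the text is incomplete there, not wrong. Timing still matters, because at 100% shift it can decide whether the remaining difference is clearly positive or near or below zero.

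**What to change.** In SAP 3.8.2.2, replace the description of the imputation model with: *The imputation model will include treatment group and all randomization strata as factors and measurements at all previous time points, including baseline, as covariates.* Alternatively, state that imputation is run separately by arm.

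In the same edit:
- name the imputed variable and its scale, and if weight in kilograms is imputed, say how a shift in percentage points is converted
- state whether the shift is applied at the first missed visit only or at every missed visit
- optionally, add a 0% shift run, which should approximately reproduce the primary estimate and so checks the code.

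The cost is a few sentences before unblinding and, if wanted, one extra run. No new data are needed, and the primary analysis does not change. The shift at which significance is lost may look more or less favourable depending on the timing rule, which is the reason to fix that rule before the data are seen.

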3.8.3. Secondary Endpoints

The secondary endpoints are:

- Proportion of subjects with $\geq 10\%$ weight gain at Week 12
- Proportion of subjects with $\geq 7\%$ weight gain at Week 12
- Change from baseline in waist circumference at Week 12
- Change from baseline in Clinical Global Impression-Severity (CGI-S) score within the ALKS 3831 Group at Week 12

3.8.3.1. Secondary Endpoint: Proportion of Subjects with $\geq 10\%$ Weight Gain at Week 12 in FAS Population

3.8.3.1.1. Analysis

The analysis will be carried out using a logistic regression model. The logistic regression model will include the treatment group, all randomization strata as factors; and the baseline weight as the covariate. The proportion of subjects with $\geq 10\%$ weight gain at Week 12 will be derived based on the same complete datasets obtained from the multiple imputation procedure as described in [Section 3.8.2.1](#) for the primary endpoint. Rubin's rule will be used to combine the results from each imputed dataset. Estimated odds ratio, 95% CI and p-value will be reported. Risk difference and 95% CI will be reported as well as the number needed to treat (NNT). NNT is calculated as the absolute value of the inverse of the risk difference, rounded up to the nearest

integer. For subjects who prematurely discontinue the study drug but are willing to come back for weight assessments, only on-treatment weight assessments will be included in the analysis.

In addition, to assess the impact of different cutoffs for weight gain (ie, 5%, 7%, 10%, etc), a plot of cumulative responder distribution at Week 12 for each treatment group will be presented. The horizontal axis will present percent weight gain, and the vertical axis will present the proportion of subjects with at least that amount of weight gain. The analysis will be based on MI for missing data.

3.8.3.1.2. Sensitivity Analysis

To assess the robustness of the analysis, the following sensitivity analyses will be performed:

- **Delta-adjusted pattern mixture model:** To assess the potential impact of missing data due to MNAR, the delta-adjusted Pattern Mixture Model will be conducted to assess the impact of missing data. Proportion of subjects with $\geq 10\%$ weight gain at Week 12 will be derived based on the same complete datasets obtained from the multiple imputation procedure of the sensitivity analysis of the primary endpoint ([Section 3.8.2.2](#)). The logistic regression model will include the treatment group, all randomization strata as factors; and the baseline weight as the covariate. It will be fitted to obtain the treatment effect estimate and standard error. Rubin's rule will be used to combine the treatment effect estimates and standard errors across imputations.
- **Including on and off-treatment assessments:** To further assess the potential impact of missing data due to MNAR, the approach described in [Section 3.8.3.1.1](#) will be repeated including both on-treatment and off-treatment weight assessments after premature discontinuation of study drug.
- **Additional covariates:** The logistic regression model may also adjust for additional covariates and/or factors, including but not limited to study sites.
- **Average treatment effect:** Average treatment difference across visits through Week 12 between ALKS 3831 and olanzapine will be analyzed.

3.8.3.2. Secondary Endpoint: Proportion of Subjects with $\geq 7\%$ Weight Gain at Week 12 in FAS Population

The analyses will be the same as proportion of subjects with $\geq 10\%$ weight gain at Week 12, including relevant sensitivity analyses ([Section 3.8.3.1](#)).

3.8.3.3. Secondary Endpoint: Change from Baseline in Waist Circumference at Week 12 in FAS Population

For the change from baseline in waist circumference at Week 12, the analysis will be the same as the primary endpoint, including relevant sensitivity analyses ([Section 3.8.2.1](#) and [Section 3.8.2.2](#)).

3.8.3.4. Secondary Endpoint: Change from Baseline in Clinical Global Impression-Severity (CGI-S) score within the ALKS 3831 Group at Week 12

To assess the change from baseline in CGI-S at Week 12 within the ALKS 3831 Group, the MMRM will be used. The model will include treatment, visit, treatment-by-visit interaction and all randomization strata as factors. An unstructured variance-covariance matrix will be used. The least squares (LS) mean, 95% CI and p-value of change from baseline at Week 12 within the ALKS 3831 Group will be reported.

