### Secondary Endpoints

The secondary endpoints are:

- Proportion of subjects with  $\geq 10\%$  weight gain at Week 12
- Proportion of subjects with  $\geq 7\%$  weight gain at Week 12
- Change from baseline in waist circumference at Week 12
- Change from baseline in CGI-S score within the ALKS 3831 Group at Week 12

For the categorical secondary endpoints of proportion of subjects with  $\geq 10\%$  and  $\geq 7\%$  weight gain at Week 12, the analyses will be carried out using a logistic regression model based on MI for missing data. The model will include the treatment group and randomization strata as factors, and the baseline weight as the covariate. For the change from baseline in waist circumference at Week 12, the analysis will be based on the ANCOVA method with MI for missing data, same as the primary analysis of the primary endpoint. For change from baseline in CGI-S within ALKS 3831 Group at Week 12, the analysis will be based on the mixed model with repeated measurements (MMRM). The model will include randomization strata, treatment, visit, and treatment-by-visit interaction term as factors; the baseline CGI-S value will be included as a covariate.

To control the overall Type I error rate, hierarchical testing will be performed in the following order: (1) percent change from baseline in body weight at Week 12, (2) proportion of subjects with  $\geq 10\%$  weight gain from baseline at Week 12, (3) proportion of subjects with  $\geq 7\%$  weight gain from baseline at Week 12, (4) change from baseline in waist circumference at Week 12, (5) change from baseline in CGI-S score within the ALKS 3831 Group at Week 12.

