3.8.4. Multiple Comparison/Multiplicity

The study will be claimed positive when the primary analysis of the primary efficacy endpoint is statistically significant. The primary endpoint will be tested at a full α level of 0.05. To control the overall Type I error rate of the primary and secondary endpoints, hierarchical testing will be performed in the following order: (1) percent change from baseline in body weight at Week 12, (2) proportion of subjects with $\geq 10\%$ weight gain from baseline at Week 12, (3) proportion of subjects with $\geq 7\%$ weight gain from baseline at Week 12, (4) change from baseline in waist circumference at Week 12, (5) change from baseline in CGI-S score within the ALKS 3831 Group at Week 12.

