Proportion of subjects with shifts in blood pressure category by visit will also be analyzed based on each subject's by-visit assessment status using the logistic regression model described above. Shifts are defined as follows:

- Proportion of subjects shifting from Normal blood pressure at baseline to Stage 1 or Stage 2 Hypertension
- Proportion of subjects shifting from Normal or Elevated blood pressure at baseline to Stage 1 or Stage 2 Hypertension

The blood pressure categories will be defined as follows based on American Heart Association criteria:

- Normal: systolic and diastolic blood pressure of < 120 and $< 80 \text{ mmHg}$, respectively
- Elevated: systolic and diastolic blood pressure of ≥ 120 to ≤ 129 and $< 80 \text{ mmHg}$, respectively
- Stage 1: systolic blood pressure of ≥ 130 to $\leq 139 \text{ mmHg}$ or diastolic blood pressure of ≥ 80 to $\leq 89 \text{ mmHg}$

- Stage 2: systolic blood pressure of ≥ 140 mmHg or diastolic blood pressure of ≥ 90 mmHg.

The following laboratory parameters will be analyzed by MMRM model as described in [Section 3.8.3.4](#). The model will include treatment, visit, treatment-by-visit interaction, all randomization strata as categorical fixed effects; the baseline value will be included as the covariate. An unstructured variance-covariance matrix will be used.

- Percent and absolute change from baseline in fasting lipids (fasting triglycerides, LDL, HDL, total cholesterol), fasting glucose, HbA1c, fasting insulin, and HOMA-IR by visit
- Percent and absolute change from baseline in additional laboratory parameters including Apo B, Apo A1, Apo B/Apo A1, hs-CRP, IL-6 and TNFa by visit.

The proportion of subjects with metabolic syndrome at each visit will be analyzed by logistic regression model including treatment group and randomization strata as factors and baseline metabolic syndrome as covariate.

The proportion of subjects meeting each individual component criterion for metabolic syndrome (listed below) will be analyzed by visit using the same logistic regression model described above with the respective baseline value for each component as the covariate.

Additionally, a similar logistic regression model including treatment and randomization strata as factors will be used to analyze the proportion of subjects shifting from no metabolic syndrome at baseline to developing metabolic syndrome postbaseline. Data are based on observed values with no imputation for missing values.

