Metabolic syndrome is defined as meeting at least 3 of the following individual component criteria:

- Waist circumference, cm > 88 (women), > 102 (men)
- Triglycerides, mg/dL ≥ 150
- HDL cholesterol, mg/dL < 50 (women), < 40 (men)
- Glucose, fasting mg/dL ≥ 100
- Blood pressure, mm Hg $\geq 130/85$

The following endpoints will be analyzed by MMRM model as described in [Section 3.8.3.4](#), as applicable.

- Change from baseline in CGI-S score (between and within treatment groups) by visit
- Change from baseline in CGI-S score (between and within treatment groups) by visit and by diagnosis
- Change from baseline in IWQOL-Lite score by visit

IWQOL-Lite scale is a 31-item self-report measure of obesity-specific quality of life. The IWQOL-Lite provides an overall total score as well as scores on five domains: (1) physical function, (2) self-esteem, (3) sexual life, (4) public distress, and (5) work. The raw IWQOL scores will be transformed as follows ([Tessier et al, 2012](#)) before analyzed by the MMRM

method. The transformed scores range from 0 to 100, with 100 representing the best and 0 the most impaired quality of life.

$$\text{Transformed Score} = \frac{\text{maximum theoretical score} - \text{actual score}}{\text{test score range}} \times 100$$

CGI-I score and CGI-I responder status (≤ 2 versus > 2) at each visit will be summarized by treatment group. Descriptive statistics will be presented.

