5. CHANGES IN CONDUCT OR PLANNED ANALYSES FROM THE PROTOCOL

If, after the study has begun, but prior to any unblinding, changes are made to primary and/or key secondary hypotheses, or the statistical methods related to those hypotheses, then the protocol will be amended (consistent with ICH Guideline E-9). Changes to exploratory or other non- confirmatory analyses made after the protocol has been finalized, along with an explanation as to when and why they occurred, will be listed in the Clinical Study Report (CSR) for the study. Post hoc exploratory analyses will be clearly identified in the CSR.

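### The SAP model for the alpha-controlled CGI-S endpoint leaves out the baseline CGI-S covariate that the protocol specifies

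*SAP*

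**What the plan says.** **SAP 3.8.3.4**, the only place in the SAP that defines this test, says: "The model will include treatment, visit, treatment-by-visit interaction and all randomization strata as factors". It adds: "An unstructured variance-covariance matrix will be used". It also says that the "p-value of change from baseline at Week 12 within the ALKS 3831 Group will be reported", along with the least squares mean and 95% CI. It names no baseline term.

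**Protocol 14.4 (Secondary Endpoints)** and the synopsis list the same factors, and then state that "the baseline CGI-S value will be included as a covariate".

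**SAP 3.8.4** places this endpoint last in the hierarchy: "5) change from baseline in CGI-S score within the ALKS 3831 Group at Week 12".

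**SAP 3.8.6** handles two groups of endpoints differently. For the laboratory parameters it refers to 3.8.3.4, restates the model, and says that "the baseline value will be included as the covariate". For by-visit CGI-S (overall and by diagnosis) and IWQOL-Lite it says only "The following endpoints will be analyzed by MMRM model as described in" 3.8.3.4, as applicable, and mentions no baseline value.

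**SAP Section 5** sets the rule for departures. If, before unblinding, "changes are made to primary and/or key secondary hypotheses, or the statistical methods related to those hypotheses, then the protocol will be amended". No departure is listed for this endpoint.

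**The concern.** A confirmatory test should have one model, fixed before unblinding. Here the protocol and the SAP give different models for the same alpha-controlled endpoint. Either could later be defended as the pre-specified one. A programmer who follows the SAP literally will fit the model without baseline.

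Baseline cannot safely be read as implied. The SAP names it in its other fully specified repeated-measures models: weight (3.8.2.2) and laboratory (3.8.6).

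Three things are at stake beyond the inconsistency:

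- **Precision.** A change score that is not adjusted for baseline carries baseline variation that the covariate would remove.
- **Between-arm comparison.** Protocol 5.3 says antipsychotic efficacy will be assessed with the CGI scales and is expected to be similar in both arms. The between-arm CGI-S model inherits the omission, so chance baseline imbalance stays in that comparison.
- **Missing data.** If sicker subjects leave more often, the model without baseline does not condition on a variable that drives missingness.

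**Working it through.** **Stated figure.** The documents give no power, SD or effect size for CGI-S. The only figure to reproduce is the primary endpoint's power of at least 90%. With 35% dropout, 200 × 0.65 = 130 per arm. The SE is 8 × √(2/130) = 0.992, and 3.5/0.992 = 3.53. Power is Φ(3.53 − 1.96) = 94.1% (94.0% by noncentral t). The claim is met, and 130 per arm is used below.

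**Formulas.** Let k = SD(Week 12)/SD(baseline) and r = the correlation between the two. In units of baseline variance/n, the variance of one arm's mean Week 12 change is:

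- without baseline: 1 + k² − 2rk
- with baseline, model-based: k²(1 − r²)
- with baseline, over repeated samples: k²(1 − r²) + (1 − rk)²/2, because the least squares mean is taken at the pooled baseline mean of two equal arms

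The first equals the second plus (1 − rk)². Omission therefore never reduces the variance, and costs nothing only when rk = 1.

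**Assumed inputs.** Baseline SD 0.8, Week 12 SD 0.95, so k = 1.1875 and k² = 1.410; n = 130 per arm.

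| | r = 0.3 | r = 0.5 |
|---|---|---|
| Variance without baseline | 1 + 1.410 − 0.7125 = 1.698 | 1 + 1.410 − 1.1875 = 1.223 |
| With baseline, model-based | 1.410 × 0.91 = 1.283 | 1.410 × 0.75 = 1.058 |
| With baseline, repeated samples | 1.283 + 0.644²/2 = 1.490 | 1.058 + 0.406²/2 = 1.140 |
| Within-arm SE, without / with (model-based) | 0.091 / 0.079 | 0.078 / 0.072 |
| Within-arm SE ratio, repeated samples | √(1.698/1.490) = 1.07 | √(1.223/1.140) = 1.04 |
| Between-arm SE (× √2), without / with | 0.129 / 0.112 | 0.110 / 0.102 |
| Between-arm SE ratio | 1.15 | 1.075 |
| Information lost, between arms | 1 − 1.283/1.698 = 24% | 1 − 1.058/1.223 = 13.5% |

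A 5000-run simulation of the between-arm contrast gave 0.127 against 0.113 and 0.110 against 0.103, or about 13% and 7%.

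**Range.**

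- Equal SDs (k = 1): the between-arm ratio is √(2/(1 + r)), which is 1.24 at r = 0.3 and 1.15 at r = 0.5. The within-arm repeated-sampling ratio is 1.10, 1.07 and 1.04 at r = 0.3, 0.5 and 0.7.
- k = 1.5: the model-based ratio falls to 1.07, 1.02 and 1.00 at the same correlations.
- A seven-visit MMRM simulation (200 per arm, r = 0.3, k = 1) gave within-arm ratios of 1.16 model-based and 1.11 empirical with no dropout, and 1.13 and 1.05 with 31% random dropout.

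**Effect on the step 5 test.** The smallest change significant at 0.05 is 1.96 × SE. Using model-based SEs, it is 0.18 points without baseline and 0.16 with it at r = 0.3, and 0.15 and 0.14 at r = 0.5.

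**Dropout related to severity.** Suppose the log-odds of dropping out rise by 0.3 to 0.5 per baseline SD, with 35% dropout. To first order, completers' mean baseline is lower by 0.3 × 0.35 = 0.105 to 0.5 × 0.35 = 0.175 SD. A completers-only mean change would then be biased by that shift × 0.8 × (1 − rk). This is 0.05 to 0.09 points at r = 0.3 (1 − rk = 0.644) and 0.03 to 0.06 at r = 0.5 (1 − rk = 0.406). The MMRM recovers part of this from earlier visits. Monotone-missing likelihood calculations put the remaining bias at about 0.01 to 0.03 points without baseline and about 0 with it. The last figure needs the baseline slope to be similar at all visits, or fitted by visit. A single common slope removes less of the bias if the baseline correlation falls over time.

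**The case against.** The strongest reply is that this is an editorial slip with little consequence. Its points, and what stands of each:

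- **Step 5 is a within-arm test, and the largest SE figures are between-arm.** This stands. The within-arm loss is smaller, and the decision would differ only if the observed change fell in a band of about 0.01 to 0.02 points. Step 5 is last, so no later test depends on it.
- **Both models test the same null, and omission does not inflate Type I error.** This stands. The estimate, SE and p-value can still differ between the two models.
- **It looks like a dropped clause.** The laboratory text in SAP 3.8.6 cites 3.8.3.4 and then lists a model with baseline, as if 3.8.3.4 contained it. This is plausible, but it explains the error without removing it. The phrase 'as applicable' for CGI-S and IWQOL-Lite does not supply a baseline term.
- **The protocol should prevail, because SAP Section 5 requires an amendment for such a change and none is shown.** This helps decide how to correct the text. It does not make the SAP's model specification correct.
- **Between-arm CGI-S is not confirmatory.** This stands: there is no non-inferiority margin or between-arm hypothesis. However, SAP 3.8.6 reports these endpoints by estimate and 95% CI, and the interval width is what the omission affects.
- **The dropout bias is small.** This stands. At 0.03 points it is under 4% of the assumed baseline SD (0.03/0.8 = 3.75%).

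**Conclusion.** The concern holds. The protocol names baseline CGI-S as a covariate, the SAP's only definition of the test omits it, no change is declared, and the by-visit CGI-S and IWQOL-Lite models inherit the gap.

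The SAP version is less precise unless rk is close to 1. How much less cannot be taken from the documents. Under the assumed SDs, with r at 0.3 and 0.5, the SE is about 15% and 7.5% larger between arms, and about 7% and 4% larger within the arm over repeated samples.

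The need for correction rests mainly on an alpha-controlled test having two conflicting specifications. A reversed conclusion at step 5 is unlikely, and the primary endpoint and steps 1 to 4 are untouched.

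**What to change.** In SAP 3.8.3.4, add baseline CGI-S as a covariate, matching Protocol 14.4. In SAP 3.8.6, state that the by-visit CGI-S models (overall and by diagnosis) and the IWQOL-Lite model each include their own baseline value.

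If the omission was intended, the SAP's own Section 5 calls for a protocol amendment before unblinding, and the reason should be given.

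The cost is one or two phrases. CGI-S and IWQOL-Lite are already collected at Visit 2, so no new data are needed, and the documents state no advantage to leaving baseline out.
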